****2. Study Procedure:****

- (1) Screen patients undergoing maintenance hemodialysis at our hospital's dialysis center whose baseline International Restless Legs Syndrome Study Group Rating Scale (IRLS) score is >15 points.
- (2) Patients who meet the inclusion criteria and are willing to sign the informed consent form.
- (3) Collect general clinical data and pre-treatment laboratory parameters, including age, gender, body mass index, Charlson Comorbidity Index score, dialysis duration, serum iron, ferritin, serum parathyroid hormone, hemoglobin, albumin, and dialysis adequacy. Assess changes in patient condition before and after treatment using scales such as the International Restless Legs Syndrome Study Group Rating Scale (IRLS), Pittsburgh Sleep Quality Index (PSQI), Hamilton Depression Rating Scale (HAMD), Hamilton Anxiety Rating Scale (HAMA), Clinical Global Impression scale (CGI), Medical Outcomes Study Sleep Scale (MOS-SS), Epworth Sleepiness Scale (ESS), and KDQOL-SF™-36.
- (4) All enrolled RLS patients will be instructed by designated personnel to orally take dipyridamole tablets, 50mg each time, three times a day, for a continuous period of 12 weeks.
- (5) Collect information on the occurrence of drug-related adverse reactions during the study period, such as nausea, headache, dizziness, diarrhea, insomnia, fatigue, bleeding, etc. The follow-up period is 12 weeks.
- (6) After the treatment concludes, collect the patients' general clinical data and laboratory parameters again.
- (7) Statistical Analysis: Measurement data conforming to a normal distribution will be expressed as mean \pm standard deviation ($\bar{x} \pm s$). Count data will be expressed as frequencies. Comparisons of means before and after treatment will be performed using paired-sample t-tests. Comparisons of rates before and after treatment will be performed using paired-sample chi-square tests. A P-value < 0.05 will be considered statistically significant. All statistical analyses will be performed using SPSS software.
- (8) Evaluate changes in patient condition before and after treatment. Primary evaluation indicators: complete remission rate, partial remission rate, overall response rate, incidence of adverse events, dropout rate.

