****I. Study Background:****

Restless Legs Syndrome (RLS) is a common complication in uremic patients, significantly impacting their quality of life and prognosis. Many studies have found that RLS is closely related to nocturnal hypertension and the occurrence of cardiovascular events in uremic patients, affects patient sleep, leads to anxiety, depression, and decreased quality of life. The mortality rate of hemodialysis (HD) patients with RLS is significantly higher than that of patients without RLS [1]. Over the past few decades, dopaminergic drugs have been the mainstay of first-line treatment for RLS. Although these drugs show significant short-term efficacy, long-term use is characterized by short half-life, susceptibility to early morning rebound, and poor long-term efficacy [2, 3]. Recent studies suggest that nucleoside equilibrative transporter inhibitors, such as dipyridamole and ticagrelor, may control RLS symptoms by increasing endogenous adenosine-mediated tonic A1 receptor activation, potentially representing a new treatment strategy for RLS [4, 5]. Preliminary clinical studies have demonstrated that dipyridamole significantly improves patients' sleep quality and quality of life [6].

We will only screen patients who meet both the inclusion and exclusion criteria to participate in this study. Enrolled patients will receive dipyridamole free of charge, 50 mg each time, three times a day, for a total of 12 weeks. During the treatment period, we will regularly follow up on

the participants' condition. Participants will need to undergo assessments using the International Restless Legs Syndrome Study Group Rating Scale (IRLS), Clinical Global Impression scale (CGI), Medical Outcomes Study Sleep Scale (MOS-SS), etc., before and after treatment to evaluate the degree of symptom change. Through this treatment, we aim to understand the specific efficacy of dipyridamole in uremic patients with RLS, the extent to which the drug improves RLS sensory and motor symptoms and sleep conditions, observe the impact of dipyridamole on concomitant depression, anxiety, quality of life, etc., in maintenance dialysis patients, and also understand the efficacy and common adverse reactions of dipyridamole in clinical use in maintenance dialysis patients.

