****Inclusion Criteria:****

- (1). Maintenance hemodialysis ≥ 3 months;
- (2). Age between 18-75 years;
- (3). Diagnosed with RLS according to the IRLSSG criteria and with an IRLS score > 15 points;
- (4). Willing to cooperate with this study.

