****3. Sample Size Calculation:****

$$\text{Formula: } n = [(Z \alpha / 2 + Z \beta) * \sigma / \Delta]^2$$

Where n is the sample size, $Z \alpha / 2$ is the two-sided quantile of the normal distribution corresponding to the significance level α (usually $\alpha = 0.05$, so $Z \alpha / 2 = 1.96$). $Z \beta$ is the quantile

of the normal distribution corresponding to the power ($1 - \beta$) (power is usually set at 0.8, so $Z\beta = 0.84$). σ is the standard deviation of the observation indicator, reflecting data dispersion. Δ is the expected mean difference before and after treatment, i.e., the minimum difference expected to be detected. Based on literature review and preliminary studies, we set $\sigma = 4$ and $\Delta = 2$. Therefore, the calculated sample size $n = 31.36$. Rounding up, $n=32$. Considering potential dropouts, the sample size needs to be increased by 10%-20%, so the final sample size is set at 80.

4. Data Analysis and Statistical Methods:

Conduct statistical analysis on the obtained data: Measurement data conforming to a normal distribution will be expressed as mean \pm standard deviation ($\bar{x} \pm s$). Count data will be expressed as frequencies. Comparisons of means before and after treatment will be performed using paired-sample t-tests. Comparisons of rates before and after treatment will be performed using chi-square tests. A P-value < 0.05 will be considered statistically significant.

Study Flowchart:

Patient Screening

↓

Collection of Patient Clinical and Laboratory Data

↓

Oral Administration of Dipyridamole Tablets under Guidance

↓ (12 weeks)

Collection of Drug-Related Adverse Reactions during the Study

↓

Post-Treatment Collection of General Clinical Data and Laboratory Parameters

↓

Statistical Analysis, Efficacy Evaluation, Manuscript Preparation

5. Safety Analysis and Content Evaluation:

Follow up and statistics on the types, number of cases, and severity grading of potential adverse reactions during dipyridamole treatment. Evaluate the causes of these adverse reactions and their causal relationship with the study drug. Calculate the incidence of adverse reactions. Main adverse reactions may include headache, dizziness, gastrointestinal discomfort (nausea, vomiting, diarrhea), hypotension, bleeding tendency, allergic reactions, etc.

6. Observation Indicators:

Primary Indicators: Restless Legs Syndrome symptom severity score (IRLS).

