****VI. Informed Consent Process:****

The informed consent process for this study will be strictly executed according to ethical norms, overseen by the project leader and research assistants to fully safeguard patient rights and the

right to informed consent.

- (1) **Implementers of Recruitment and Informed Consent:** The recruitment and informed consent process for this study is primarily the joint responsibility of the project leader and research assistants. Research assistants are responsible for preliminary screening of patients against the inclusion and exclusion criteria and assisting the project leader in communicating study details to patients.
- (2) **Specific Informed Consent Process:** After screening, the project leader or research assistant will conduct a face-to-face discussion with the patient, detailing the study's purpose, procedures, potential risks, and benefits, ensuring the patient fully understands the study. Provide the patient with a written informed consent form that is easy to understand, avoiding excessive technical terminology, ensuring the patient can read and comprehend it independently. Allow the patient ample opportunity to ask questions, and provide detailed answers to all queries, ensuring transparency and adequacy of the informed consent process.
- (3) **Requirements for the Informed Consent Subject:** All subjects must be adults aged 18 or older with full capacity; no proxy signatures are required. The research team ensures voluntary participation and will absolutely not exert any form of pressure or inducement for patients to participate.
- (4) **Avoiding Direct Recruitment by Treating Physician:** To avoid potential conflicts of interest or implicit pressure, the patient's treating physician will not participate in the informed consent process. Other members of the research team will communicate and explain the study content to the patient.
- (5) **Voluntariness and Withdrawal Guarantee:** The informed consent form clearly states that participation is entirely voluntary, and the patient can unconditionally withdraw from the study at any stage, which will not affect their subsequent medical care. If a patient chooses to withdraw, the research team will provide necessary medical advice and ensure a smooth withdrawal process without additional burden.

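### The protocol does not require a pre-treatment IRLS rating separate from the >15 qualifying score; reusing that score as 'before' would comply and let regression to the mean count as improvement

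*Protocol*

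**What the plan says.** - **Entry.** Protocol III.1, inclusion criterion (3), requires "Diagnosed with RLS according to the IRLSSG criteria and with an IRLS score > 15 points".
- **Label.** III.2 Study Procedure, item (1), screens patients "whose baseline International Restless Legs Syndrome Study Group Rating Scale (IRLS) score is >15 points". This is the only IRLS score that the protocol calls baseline, and it is the score that selects the patient.
- **Pre-treatment assessment.** The Background states "Participants will need to undergo assessments using the International Restless Legs Syndrome Study Group Rating Scale (IRLS" and two other scales, before and after treatment. III.2 item (3), which follows the consent step in item (2), says "Assess changes in patient condition before and after treatment using scales such as the International Restless Legs Syndrome Study Group Rating Scale (IRLS" and seven further scales. Section VI item (2) has "After screening, the project leader or research assistant will conduct a face-to-face discussion with the patient".
- **Outcome and test.** III.6 names IRLS as the primary indicator. III.2 item (7) says "Comparisons of means before and after treatment will be performed using paired-sample t-tests". III.1 describes a single-center, self-controlled study, so there is no concurrent group.
- **Rates.** III.2 item (8) adds "Primary evaluation indicators: complete remission rate, partial remission rate, overall response rate, incidence of adverse events, dropout rate". The protocol does not define remission or response.

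No passage says that the pre-treatment IRLS is a new rating, how long after the qualifying rating it is taken, or which score is the 'before' value.

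**The concern.** When patients enter because a measured score exceeds a cut-off, some of them are above it partly through a chance high reading. Their later scores tend to be lower even if nothing has changed. If the selecting score is also the starting value for change, that fall enters the paired difference as improvement. With no control group, nothing subtracts it.

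Efficacy is a stated objective, and this bias runs in the drug's favour. An analysis plan can choose between two pre-dose scores, but it cannot create a rating that was never taken. With only one pre-dose score, a correction would have to rely on an assumed or external reliability.

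**Working it through.** **The plan's own figure.** III.3 gives n = [(1.96 + 0.84) × 4 / 2]² = 5.6² = 31.36, rounded up to 32. This reproduces. The final size is 80. The same section supplies sigma = 4 and delta = 2.

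**Smallest significant fall.** With SD of change 4, it is t(0.975, n−1) × 4 / √n. That is 0.89 points at n = 80, and 1.00 at n = 64 (80 less the protocol's upper dropout allowance of 20%).

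**Inputs for the regression.** The cut-off of 15, sigma = 4 and n = 80 come from the protocol. The mean (mu) and SD (s = 6) of IRLS among screened patients are not in the documents and are assumed, as is normality. In the main case sigma is read as the SD of change, and all of that variation is treated as independent rating error. The error variance per rating is then sw² = 4²/2 = 8, and the implied test-retest correlation is 1 − 8/36 = 0.78.

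**Formula.** If the qualifying score is the 'before' value and the drug does nothing:

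expected fall = (sw²/s) × phi(z) / (1 − Phi(z)), with z = (15 − mu)/s.

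Example at mu = 20: z = −0.833, phi = 0.282, 1 − Phi = 0.798, so the fall is 1.333 × 0.353 = 0.47.

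Rejection is the share of 20,000 simulated trials with P < 0.05 in the two-sided paired t-test, with no drug effect:

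| Pool mean | Expected fall | Rejection, n = 80 | Rejection, n = 64 |
|---|---|---|---|
| 28 | 0.05 | 5.1% | 5.0% |
| 26 | 0.10 | 5.3% | 5.4% |
| 24 | 0.19 | 6.7% | 6.5% |
| 22 | 0.31 | 10.7% | 9.1% |
| 20 | 0.47 | 19.3% | 15.8% |
| 18 | 0.68 | 33.6% | 28.6% |
| 12 (extreme) | 1.52 | 93.8% | 87.7% |

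At n = 80, rejections in the drug's favour (nominal 2.5%) are 10.4% at mean 22 and 19.1% at mean 20. The share of screened patients at or below the cut-off, Phi(z), is about 31% at mean 18 and 69% at mean 12.

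**Sigma read as the SD of the score.** III.3 words sigma as the SD of the observation indicator, so this reading is also open. Then s = 4 and sw² = 16 × (1 − r), where r is the test-retest correlation. For pool means 18 / 20 / 22:

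- r = 0.8: fall 0.31 / 0.16 / 0.07; rejection 20% / 9% / 6%
- r = 0.5: fall 0.78 / 0.41 / 0.18; rejection 45% / 16% / 7%

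**With a second pre-dose rating** (main case, n = 80). If its error has correlation rho with the error of the qualifying rating, the expected fall shrinks to rho times the value in the table. Rejection at rho = 0 / 0.25 / 0.5:

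- Mean 22: 5.1% / 5.5% / 6.4%
- Mean 20: 5.3% / 5.6% / 8.1%
- Mean 18: 5.0% / 6.7% / 11.9%
- Mean 12: 5.3% / 13.5% / 39.6%

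**If the second rating must also exceed 15.** A separate check assumed mean 15, SD 6 and correlation 0.8. Reusing the qualifying score gave a fall of 0.96. A new rating not used for eligibility gave about 0. A new rating that also had to exceed 15 still left about 0.60.

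**The case against.** The strongest reply is that the procedure already implies a second rating. III.2 runs in order: screening on IRLS, consent, pre-treatment data and scales, dosing. Section VI places the consent discussion after screening. On that reading the qualifying score is not the one analysed. This is a fair reading and it stands as a possibility. It does not close the gap, because item (1) gives the name 'baseline' to the qualifying score and that single score would also satisfy an assessment before treatment.

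A reader might go further and infer that the protocol will analyse the qualifying score. The documents do not say so; the text is ambiguous. A reader might also take the flowchart as proof, since between screening and dosing it shows only "Collection of Patient Clinical and Laboratory Data". That inference fails. The post-treatment box names no scale either, and a post-treatment IRLS is plainly intended, so the flowchart simply leaves scales out.

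Three further points stand:

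- Which of two pre-dose scores is analysed may be left to an analysis plan. Whether a second one is collected may not.
- The size depends on an assumed pool and on treating all variation in change as rating error. If part of it is true variation in change between patients, the fall is smaller.
- The rejection rates isolate one mechanism. They are not this study's overall false-positive rate, because placebo response and natural course act on the same comparison.

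Item (8) is affected only if remission and response are based on IRLS, which the protocol does not state.

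**Conclusion.** The point holds as a conditional one. The protocol permits one IRLS score to serve as both entry criterion and 'before' value of the primary comparison, and if that is done the bias favours the drug.

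Under the main assumptions the fall is 0.05 to about 0.7 points for pool means from 28 to 18, at most about a third of the planned difference of 2 (0.68/2 = 0.34). It is below the 0.89 needed for significance, yet at the lower pool means it raises rejection well above 5%, to about 34% at mean 18. It is negligible if nearly all screened patients score far above 15. It grows as more of them fall near or below the cut-off, or if the scale's reliability is lower.

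A large, established bias cannot be inferred, because the documents give neither the distribution of screened scores nor the reliability of the scale. The case for acting is that the remedy is cheap and is available only before dosing.

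**What to change.** Amend III.2 items (1) and (3):

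- Use the >15 score for eligibility only.
- Take a separate IRLS rating after consent and before the first dose, at a stated interval from the qualifying rating.
- Use that second score, whatever its value, as 'before' in the IRLS change analysis, and in any remission or response rate that is based on IRLS. Requiring it to exceed 15 again would bring back part of the bias.
- If item (3) already means this, say so and give the interval.

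**Cost.** One extra questionnaire per patient at a routine dialysis attendance, a short delay to the first dose, and some analysed patients with a 'before' score of 15 or less. No extra patients are needed. If a second rating is already intended, the cost is one sentence.

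**Limits.** Regression to the mean is fully removed only if the errors of the two ratings are independent, so the interval matters. Placebo response and natural course remain, and the change still cannot be attributed to the drug alone.

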Secondary Indicators: Quality of life score (KDQOL-SF-36), Clinical Global Impression scale (CGI) score, Medical Outcomes Study Sleep Scale (MOS-SS) score, Pittsburgh Sleep Quality Index (PSQI) score, Epworth Sleepiness Scale (ESS) score, Hamilton Anxiety Rating Scale (HAMA) score, Hamilton Depression Rating Scale (HAMD) score, Self-Rating Anxiety Scale (SAS) score, Self-Rating Depression Scale (SDS) score.

Safety Indicators:

- ① Occurrence of adverse reactions: including but not limited to headache, dizziness, gastrointestinal discomfort (nausea, vomiting, abdominal pain, diarrhea), hypotension, bleeding

tendency (gingival bleeding, epistaxis, subcutaneous bruising, etc.), allergic reactions (rash, pruritus, dyspnea, etc.).

② Laboratory parameter monitoring:

* Hematological indicators: Regularly test complete blood count (including red blood cell count, hemoglobin, platelet count, etc.) and coagulation function (prothrombin time, activated partial thromboplastin time, fibrinogen, etc.) to monitor whether dipyridamole's antiplatelet aggregation effect increases bleeding risk or causes hematological abnormalities.

* Biochemical indicators: Test liver and kidney function parameters (e.g., ALT, AST, serum creatinine, blood urea nitrogen, etc.) to assess the drug's impact on liver and kidney function; monitor electrolytes (e.g., potassium, sodium, chloride, etc.) to observe if drug effects or changes in uremia condition lead to electrolyte disturbances.

③ Vital signs monitoring:

* Monitoring content: Regularly measure patients' blood pressure, heart rate, respiratory rate, body temperature, and other vital signs, with particular attention to blood pressure changes, alert for hypotension caused by the vasodilatory effect of dipyridamole.

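### Safety collection in III.2(5) and the flowchart is limited to reactions already called drug-related, which conflicts with the adverse-event incidence in III.2(8) and the later causality step in III.5

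*Protocol*

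**What the plan says.** Two places in the protocol tell staff which clinical safety data to gather. Item (5) of III.2 (Study Procedure) says to "Collect information on the occurrence of drug-related adverse reactions during the study period" and gives an open list of examples: "such as nausea, headache, dizziness, diarrhea, insomnia, fatigue, bleeding, etc". The Study Flowchart, which follows III.4, has the step "Collection of Drug-Related Adverse Reactions during the Study".

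Item (8) of III.2 then lists the primary evaluation indicators, which end with "overall response rate, incidence of adverse events, dropout rate". That item sets no limit on cause.

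III.5 (Safety Analysis and Content Evaluation) calls for counting the types, number and "severity grading of potential adverse reactions during dipyridamole treatment", and then says: "Evaluate the causes of these adverse reactions and their causal relationship with the study drug". It goes on to calculate an incidence, which it words in terms of reactions. III.6 (Observation Indicators) names as its first safety indicator "Occurrence of adverse reactions: including but not limited to headache, dizziness" and further symptoms. It adds regular laboratory tests and vital signs. For electrolytes it leaves the cause open, the aim being "to observe if drug effects or changes in uremia condition lead to electrolyte disturbances".

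**The concern.** Relatedness to the drug is a judgement. III.5 makes it after the data are in; III.2(5) and the flowchart, as worded, make it the condition for recording anything. If staff follow the collection step to the letter, an event that the person taking the history attributes to dialysis, uremia or another illness never reaches the record.

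Two results are then at stake. The incidence of adverse events in III.2(8) would count only events screened as related. The causality assessment in III.5 would become one-sided: it could reclassify a recorded event as unrelated, but could not recover one that had been screened out.

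The study is single-centre and self-controlled (III.1), so no control group shows how often such events occur without the drug. The first impression of cause therefore cannot be checked against a comparison group. Nor can an analysis plan repair the loss, because it arises when the data are collected.

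**Working it through.** The protocol states no event rate that could be reproduced, so the check is mainly a comparison of the passages.

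**Step 1: what each place covers.**

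| Place | Role | Term used | Limit on cause |
|---|---|---|---|
| III.2(5) | collection | adverse reactions | drug-related |
| Flowchart | collection | adverse reactions | drug-related |
| III.2(8) | reported indicator | adverse events | none |
| III.5 | follow-up, grading, causality | potential adverse reactions | cause assessed afterwards |
| III.6, first safety indicator | indicator | adverse reactions, open list | none stated |
| III.6, laboratory and vital signs | measurement | values | none |

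The two rows that direct collection are the only two carrying the drug-related qualifier.

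**Step 2: is there another route for recording events whatever their cause?** Laboratory values and vital signs are measured regardless of cause. So are the scales applied before and after treatment (III.2(3) and III.6), which cover RLS severity, sleep, sleepiness, mood, global impression and quality of life. Section IV asks patients to tell the physician about bleeding and similar events, but sets no rule for recording them. Beyond these, no passage provides for recording clinical events regardless of cause.

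**Step 3: direction.** Let N be the patients followed, A the number with at least one event of any cause, and R the number with at least one event judged related when the record is made. Anyone counted in R is also counted in A, so R ≤ A. The incidence under literal collection is R/N, the all-event incidence is A/N, and the shortfall is (A − R)/N, which is at least 0.

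**Step 4: size.** The protocol gives neither A nor R, so the shortfall cannot be estimated. As a unit of scale only: if the denominator is the planned 80 patients, each patient whose only events were left out lowers the incidence by 1/80 = 1.25 percentage points. If staff record everything and judge afterwards, R is not used as a filter and the shortfall is 0.

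**The case against.** The strongest reply is that the drug-related wording is not meant as a filter. III.5 speaks of potential reactions and then asks for their causes, a step with little left to judge if only related events had been gathered. III.6 has an open list without the qualifier. On this view III.2(5) is a one-line summary and the flowchart entry a label. The terms are also used loosely: bleeding is an example of a reaction in III.2(5) and an adverse event in section IV, and section VII describes adverse events as drug-related. The objective in section II, III.5 and III.6 all speak of reactions, so within section III the odd term out is the one in III.2(8), and renaming it might seem enough.

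Much of this stands. The filter is one literal reading, and III.5 does imply recording first and judging later. But the instruction that staff would follow says otherwise, and neither III.5 nor III.6 says that events are recorded whatever their cause. Renaming the III.2(8) item would align the labels but leave relatedness as the entry condition, still in conflict with the order in III.5.

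Two stronger readings are tempting and should be resisted:

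- A reader might infer that symptoms are recorded only if blamed on the drug. That is too broad, because the before/after scales capture several symptoms regardless of cause.
- A reader might cite insomnia as a symptom that would be lost, since section I says RLS itself disturbs sleep. The protocol does not support this: insomnia is named for collection in III.2(5), and sleep is scored with PSQI and MOS-SS in any case.

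**Conclusion.** The conflict is real. The collection rule does not match the indicator in III.2(8) or the order of steps in III.5. It is more than a matter of terms, because an event left out during the 12 weeks is lost for good.

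The consequence is conditional. It assumes that III.2(5) is applied as worded and that some clinical events are thought unrelated when they occur. If both hold, the III.2(8) incidence is understated wherever a patient's only events were screened out, by an amount the protocol does not allow one to estimate. If staff already work as III.5 implies, the effect is zero. A reader might conclude that unrelated-looking events will go unrecorded; the text shows only that it permits this. Laboratory and vital-sign monitoring and the scales are not affected. The change should be made because it is cheap and the possible loss is irreversible, but the point does not show that the safety results will be wrong.

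**What to change.** In III.2(5) and the flowchart, delete drug-related as the condition for collection. State instead that all adverse events during the 12 weeks are recorded regardless of suspected cause, with the existing symptom list kept as examples. Say that severity and relatedness are assessed after recording, as III.5 describes. Use the same terms in III.2(5), III.2(8), III.5 and III.6: adverse event for anything recorded, adverse reaction for those later judged drug-related. Report both incidences.

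The cost is a few more entries on the case report form and possibly a higher reported event rate, which readers can interpret because the drug-related figure would stand beside it.

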****III. Study Design and Methods:****

****1. Study Population:**** This is a single-center, self-controlled study. We plan to recruit 80 patients with uremia and RLS who are undergoing maintenance hemodialysis at the Blood Purification Center of the First Affiliated Hospital of Chongqing Medical University from July 2025 to December 2025.

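### Symptomatic adverse reactions are recorded only on drug, so the causality judgement and the adverse-event incidence have no pre-treatment symptom record behind them

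*Protocol*

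**What the plan says.** All places are in the Protocol.

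- **Design (III.1).** "This is a single-center, self-controlled study". There is no concurrent control group.
- **Collection (III.2, item 5).** "Collect information on the occurrence of drug-related adverse reactions during the study period, such as nausea, headache, dizziness, diarrhea, insomnia, fatigue, bleeding, etc". The same item adds: "The follow-up period is 12 weeks", which equals the treatment period. The flowchart puts this collection after dosing has started.
- **Analysis (III.5).** It covers the types, number of cases and "severity grading of potential adverse reactions during dipyridamole treatment". It then asks the team to "Evaluate the causes of these adverse reactions and their causal relationship with the study drug" and to "Calculate the incidence of adverse reactions".
- **Safety indicators (III.6).** Hypotension and minor bleeding (gums, nose, bruising) join the list. Blood pressure is to be watched, "alert for hypotension caused by the vasodilatory effect of dipyridamole". Measurements are to be regular, but no pre-treatment reading is named.
- **Baseline (III.2, item 3).** Demographics, comorbidity, several laboratory values including hemoglobin, and the rating scales, among them PSQI, MOS-SS, ESS and KDQOL. Symptoms and vital signs are not named.
- **Primary evaluation indicators (III.2, item 8).** These include adverse-event incidence, worded without any restriction to drug-related events.

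**The concern.** In a self-controlled study the patient's own pre-treatment state is the only comparator. The plan collects it for efficacy but not for the symptoms that make up most of the adverse-reaction list.

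The Protocol itself shows that illness and drug reaction can look alike. The background section says RLS "affects patient sleep, leads to anxiety, depression, and decreased quality of life", and insomnia is then listed as a drug reaction. For electrolytes, III.6 explicitly allows that the uremia, and not the drug, may be the cause.

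An assessor who does not know whether a patient was already nauseous, tired or dizzy before the first tablet can err either way: by charging an old symptom to the drug, or by dismissing a real reaction as part of the illness. Adverse reactions are named in the Section II objective and adverse-event incidence is a primary evaluation indicator, so the error would reach a headline result. A later analysis plan cannot repair it, because symptoms that were not asked about before dosing cannot be reliably recovered afterwards.

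**Working it through.** **Plan's own figure.** The plan gives no number on this point. Its only calculated figure is the efficacy sample size: [(1.96 + 0.84) × 4 / 2]² = 5.6² = 31.36, rounded up to 32. It reproduces and has no bearing here. The planned N of 80 is used below only to turn percentages into patients.

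**Which safety items have a baseline?**

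| Item | Pre-treatment record in the Protocol |
|---|---|
| Hemoglobin | Yes: III.2(3), laboratory values repeated under III.2(6) |
| Sleep disturbance | Yes, on scales (PSQI, MOS-SS, ESS), but not linked to the insomnia count |
| Active bleeding | Excluded at entry (exclusion 2) |
| Minor bleeding (gums, nose, bruising) | No history recorded |
| Nausea, headache, dizziness, diarrhea, fatigue | None named |
| Blood pressure, hypotension | None named |

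**Illustration of size.** The two rates are assumptions; the Protocol gives neither.

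- b = share of patients who have the symptom anyway; range 5% to 40%.
- d = share of the remaining patients in whom the drug causes it; 5%.
- Crude on-drug incidence = 1 − (1 − b)(1 − d) = b + d(1 − b).
- Drug-emergent incidence = d(1 − b).
- Background share of the crude figure = b / crude.

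| b | Crude | Drug-emergent | Background share | Crude vs drug-emergent patients, N = 80 |
|---|---|---|---|---|
| 5% | 0.05 + 0.05 × 0.95 = 9.75% | 4.75% | 51% | 7.8 vs 3.8 |
| 10% | 0.10 + 0.05 × 0.90 = 14.5% | 4.5% | 69% | 11.6 vs 3.6 |
| 20% | 0.20 + 0.05 × 0.80 = 24% | 4% | 83% | 19.2 vs 3.2 |
| 40% | 0.40 + 0.05 × 0.60 = 43% | 3% | 93% | 34.4 vs 2.4 |

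With no drug effect at all (d = 0), the on-drug count is 80 × b: 4, 8, 16 and 32 patients.

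**With a causality review.** The table assumes that every background symptom is counted. If the III.5 review wrongly attributes a share m of background cases to the drug, the false count is 80 × b × m. At b = 20%, m = 25% gives 80 × 0.20 × 0.25 = 4 patients (5%), and m = 50% gives 8 patients (10%). At b = 10% these fall to 2 and 4 patients. The review shrinks the error, but how far depends on m, and a baseline symptom record is what would keep m low.

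**The case against.** A reader might infer that safety has no baseline at all. The documents do not support that. Hemoglobin is measured before treatment and laboratory values are repeated after it, sleep is scored on scales before treatment, and active bleeding bars entry. Insomnia, the most obvious overlap, is the best covered item. This objection stands, and the point is limited accordingly.

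A reader might also infer that background illness is certain to be mixed into the result. For drug-related reactions it is not: III.5 requires a causal assessment, so mixing there is a risk. It is direct only for the adverse-event incidence in III.2(8), which carries no causality filter.

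Further objections:

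- **Background rates are outside knowledge.** Correct. Sleep disturbance is the only listed symptom that the Protocol itself ties to the enrolled disease. It gives no rate for fatigue, nausea, hypotension or bleeding, so the illustration cannot be read as an estimate. At b = 20% the crude figure is six times the drug-emergent one, but only with assumed rates and no causality review.
- **General clinical data might include symptoms and vital signs.** The wording of III.2(3) allows it but does not require it.
- **Past episodes are recoverable.** In part. Section VIII names medical records as a source and Section VII says patients are under regular treatment at the unit, so earlier hypotension or bleeding may be on file. That does not extend reliably to nausea, headache or fatigue.
- **A new-or-worse definition belongs in the analysis plan.** The definition may, but the baseline data it needs must be collected under the Protocol.

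**Conclusion.** The point holds for symptomatic reactions and vital signs. They are counted only on drug, in a study whose sole comparator is the patient's own earlier state, and no pre-treatment record of them is required. The causality evaluation is planned but lacks its main input, and the all-cause adverse-event incidence absorbs any pre-existing symptom in full.

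The size is unknown. Under assumed background of 10% to 20% and 5% drug-caused, crude incidence is 14.5% to 24% against 4.5% to 4% drug-emergent. That assumes pre-existing symptoms persist and are all counted; a working causality review would narrow the gap. The opposite error, a real reaction dismissed as background, is possible but is not sized here. The change is worth making because it is cheap and the information cannot be reliably recovered later.

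**What to change.** 1. **III.2(3):** before the first tablet, ask once for every symptom listed in III.2(5) and III.6, with severity, and record vital signs.
2. **III.5:** have the causality assessor use that record, and use the baseline PSQI and MOS-SS when judging insomnia.
3. **III.5 and III.2(8):** report events that are new or worse than pre-treatment, and use one term throughout in place of adverse events in one section and drug-related adverse reactions in another.
4. **Optional, for hypotension and bleeding only:** add a before-versus-during rate per dialysis session from the unit's own records, where they exist, over a fixed pre-treatment window.

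**Limits.** A single baseline question does not give a matched before rate for the other symptoms. Background symptoms that first appear during the 12 weeks will still count as new and still need the causality judgement.

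**Cost.** A few minutes per patient and some chart extraction. Pre-existing symptoms that do not change will no longer count as reactions.
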